#### 7.2 Enrollment/Baseline

All participants will download the app, complete the Baseline survey through the app via SurveyGizmo API, and provide contact information for a friend or relative. Intervention participants will also receive access through the app to basic prevention services (HIV test planning and test locators; risk assessment; HIV treatment locators; and condom, HIV test kit, and at-home STI specimen collection kit distribution) plus monthly PrEP eligibility assessments, PrEP provider locator, enhanced information about PrEP, and referrals to local PrEP navigators. The app also provides links to health insurance exchanges, where men can seek health insurance (all cities) or payment assistance programs. The control arm will be referred to existing online PrEP and HIV prevention information (Appendix C). Participants who do not download the app or have problems downloading the app will be ineligible to participate in the study.

# 7.3 Follow-up Visits

All participants will be asked to complete quarterly surveys through the app for follow-up visits at Month 3, 6, 9 and 12. Participants who have indicated starting PrEP will be asked to upload a picture of their prescription and/or be asked to self-collect DBS using a home test kit.

Both groups will also receive a monthly assessment. The intervention group will receive a monthly PrEP assessment and the Control group will receive a survey about diet and exercise of similar length. All participants will also be asked questions to ascertain whether they started PrEP within the past month. Generic questions about new medication prescriptions will be used in the control arm so that PrEP is not mentioned specifically. Intervention arm participants will be asked if they have initiated PrEP prior to starting the monthly PrEP assessment. Participants reporting PrEP initiation will then complete a PrEP adherence assessment.

The intervention group will be able to use the resources in the app throughout the study, including placing orders for home test kits, condoms and lubricant.

#### 7.4 Withdrawal Visit

Participants may withdraw at any time during the study. If they indicate they wish to withdraw, they will be asked to complete a short survey to identify reasons for wanting to withdraw.

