# 3.2 Study Outcome Measures

# 3.2.1 Primary

The rate of PrEP uptake will be assessed during follow-up by self-report at months 3, 6, 9, and 12. Self-report will be confirmed by laboratory testing for the presence of tenofovir diphosphate (TFV-DP) and/or photograph of PrEP prescription or bottle.

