#### 5.2.2 Retention

The study retention plan will incorporate multiple interventions to achieve a retention rate greater than 70%. Contact information will be collected from each participant, including email and mobile phone number verification. The study will allow participants to schedule their preference for when (e.g., afternoon, evening) they would like to receive prompts to complete electronic follow-up surveys. Participants are more likely to complete surveys if they are alerted about them at a time they can complete the survey. At enrollment, study staff will ask permission for several means of contacting participants and ask for updated information on each follow-up survey. Retention contacts will be customized based on participants' contact preferences (email, text, call, US mail) and organized on a database platform called Study Management and Retention Tool (SMART), a secure system accessible only to designated study staff. Participants will be asked about any changes in their contact information or plans to move during each follow-up survey, conducted at 3-month intervals.

Follow-up methods include sending electronic notification reminders to the participant up to 3 times if a survey remains uncompleted. If after the 3rd notification, the assessment has

still not been completed, then the retention activities will escalate to a staff member. Depending on the participant's preferences provided upon registration, contacts will be made initially with the preferred mode of re-contact (for example, SMS); if still unresponsive, other available modes (e.g., phone call, private social media messages) will be used. Each contact is logged in an electronic retention system developed by Emory. The system maintains electronic lists of each participant's retention status and automatically creates notification lists for retention staff to ensure that a systematic process is followed and documented for retention.

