# 5.4 Subject Withdrawal

Participants may voluntarily withdraw from the study for any reason at any time. The study investigators also may withdraw participants from the study in order to protect participant or staff safety. Study staff will record the reasons for all withdrawals or holds from the study on a Study Stop Form in the participants' study records.

Participants who seroconvert will be asked to participate in in-depth interviews (IDI). All of the participants will be followed per standard protocol for linkage to care. Participant will then be withdrawn from study activities.

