#### 7.5 Unscheduled Visit

Any interaction with participants between scheduled visits will be considered unscheduled visits and will be tracked in SMART.

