# 14.1 Recontacting Past Participants

Participants who reported PrEP initiation on a monthly check-in survey but not a quarterly survey (primary study outcome) will be contacted for clarification. Only the participants who previously provided consent to be recontacted will receive a message. A \$20 compensation in the form of electronic gift code will be given to those participants who respond.

Voicemail: Hi, this is [insert your name] calling from Emory with the HealthMindr study. You have reported starting PrEP during our research study, but you also reported that you have not started PrEP in surveys afterwards. I was hoping to verify some information from your time in the study. You are eligible to receive additional compensation for your response. You can call us back at [phone number]. Or feel free to text me and let me know what the best time is for a call. Thank you!

Phone Script: Hello, may I speak with [PARTICIPANT'S NAME]? My name is [insert your name]. I am with Emory working on the HealthMindr study. You have reported starting PrEP during our research study, but you also reported that you have not started PrEP in surveys afterwards. According to your survey, you reported PrEP usage in [MONTH/YEAR]. Is this correct? Did you stop taking PrEP any time after?Thank you for your clarification. Also for the compensation, we will send you a \$20 gift code. Do you have a preferred store? We have gift codes from Amazon, Target and Walmart.That is all the questions I have and thank you for participating in our research study!

Text Message: Hello! This is [NAME] from the Emory HealthMindr study. We were hoping to get you on a call for a few minutes to to verify some information from your time in the study and you will be compensated for your time. What time works best for you for a short phone call?

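### The withdrawal survey has no stated PrEP question, so a start after a leaver's last answered survey goes unrecorded (low severity)

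*Combined protocol and SAP*

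**What the plan says.** Section 7.4 gives the withdrawal survey one purpose: "they will be asked to complete a short survey to identify reasons for wanting to withdraw". Section 5.4 adds a staff record with the same content: "Study staff will record the reasons for all withdrawals or holds from the study on a Study Stop Form".

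The primary outcome has no withdrawal time point. Section 3.2.1 states: "The rate of PrEP uptake will be assessed during follow-up by self-report at months 3, 6, 9, and 12". Between those surveys, Section 7.3 has a monthly check in both arms: "All participants will also be asked questions to ascertain whether they started PrEP within the past month". It is asked directly in the intervention arm and through generic new-medication questions in the control arm. Section 5.2.3 sends a dried blood spot (DBS) kit to men who report a start and asks them for a photograph.

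Section 14.1 labels the quarterly survey the primary study outcome and follows up discordant reports: "Participants who reported PrEP initiation on a monthly check-in survey but not a quarterly survey (primary study outcome) will be contacted for clarification". Only men who had agreed to recontact are approached.

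For other contacts, Section 7.5 says: "Any interaction with participants between scheduled visits will be considered unscheduled visits and will be tracked in SMART". In Section 5.2.2, after three unanswered notifications, "the retention activities will escalate to a staff member". Neither section names a PrEP question. Section 12.3 deals with loss to follow-up by censoring and gives no rule for the censoring date.

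**The concern.** A man who withdraws formally is in contact with the study and is completing a survey, yet nothing in the plan has him asked the one question on which the primary analysis depends. If he started PrEP after his last answered survey, that start is lost. The recontact procedure in Section 14.1 cannot recover it, because it begins from a start already reported on a monthly survey.

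Two things are at stake. The first is completeness: few starts are expected, particularly in the control arm. The second is validity: the survival analysis treats leaving as unrelated to starting PrEP. In a trial of PrEP uptake, a man who has started may see no reason to continue, and this could differ between arms. Without a PrEP item at exit, the trial has no data on leavers with which to examine that.

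**Working it through.** **Inputs** (Section 12.2 unless stated): 438 intervention and 219 control men; 12-month uptake of 9% and 2%; 20% annual attrition; two-sided α of 0.05 (the sidedness is assumed). The Section 5.2.2 retention target is above 70%, so attrition could approach 30%.

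**1. The plan's own figure.** Remove 20% from each arm (350.4 and 175.2 men) and compare 9% with 2%, using pooled variance under the null.
- Pooled proportion: (2 × 0.09 + 0.02)/3 = 0.0667.
- Standard error: 0.02308 under the null, 0.01859 under the alternative.
- z = (0.07 − 1.96 × 0.02308)/0.01859 = 1.33, so power is 90.9%. The plan states 91%.

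The same method gives 82.7% and 70.4% for the 4-fold and 3.5-fold effects, against the stated 80% and 74%. The match to the headline figure therefore does not establish which method the sponsor used. Nothing below depends on it.

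**2. Expected starts with attrition.** Yearly hazards are λ = −ln(0.91) = 0.0943 and −ln(0.98) = 0.0202; the attrition hazard is μ = −ln(0.8) = 0.2231. Expected starts = n × λ/(λ+μ) × (1 − e^−(λ+μ)).
- Intervention: 438 × 0.2971 × 0.272 = 35.4.
- Control: 219 × 0.0830 × 0.216 = 3.9.
- Total: about 39.

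**3. Starts hidden at withdrawal if leaving is unrelated to PrEP.** The documents do not separate formal withdrawal from silent loss. As an upper end, let every lost man withdraw formally: 0.2 × 438 = 87.6 and 0.2 × 219 = 43.8. Hidden starts = leavers × (1 − e^(−λw/12)), where w is months since the last answered survey.

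| Gap w | Intervention | Control | Total |
|---|---|---|---|
| 0.5 month (mean, monthly surveys answered) | 0.34 | 0.04 | 0.38 |
| 1.5 months (mean, quarterly only) | 1.03 | 0.11 | 1.14 |
| 3 months (full quarter missed) | 2.04 | 0.22 | 2.26 |

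If half of the attrition is formal withdrawal, the totals are 0.19, 0.57 and 1.13. At 30% attrition, all formal, they are 1.5 times the table: 0.57, 1.71 and 3.39.

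**4. Balance between arms.** At the 1.5-month gap the loss is 1.03/35.4 = 2.9% of intervention starts and 0.11/3.9 = 2.8% of control starts. Leaving that is unrelated to PrEP therefore costs the arms nearly the same proportion.

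**5. Effect on power at a hazard ratio of 4.5.**
- Schoenfeld, Φ(√(d × 2/9) × ln 4.5 − 1.96): 99.35% at d = 39.3 and 99.45% with one more event. This formula is close to its ceiling here.
- Freedman, Φ(√(2d) × 3.5/10 − 1.96): 87.4% at d = 39.3, 88.2% with one more event and 89.1% with 2.26 more.

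On either formula one recovered start adds less than one percentage point, and the full-quarter case adds less than two.

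**The case against.** The strongest reply is that both arms are asked about PrEP every month, that a reported start triggers a confirmation request, and that discordant reports are followed up. This stands in large part. A man who answers his monthly surveys is unobserved for at most about a month before he leaves. It does not close the gap: a man who is disengaging may already be skipping monthly surveys, and Sections 3.2.1 and 14.1 tie the primary outcome to the quarterly ones.

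Second, the withdrawal form is not in the documents, so the absence of a PrEP item is inferred from the purpose stated in Section 7.4. That is fair. If the item is on the form, the protocol should say so and say whether it counts.

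Third, informative leaving is conjecture. Section 5.2.3 gives starters some reason to stay: $40 for a DBS specimen, $15 for a photograph, and $60 for the month 12 survey. If intervention-arm starters did leave preferentially, the loss would work against the app and would not create a false positive. This stands too; the documents settle neither the rate nor the direction.

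Several stronger readings are tempting, and the documents do not support them:
- A reader might infer that several starts, perhaps 4 to 8 in the intervention arm, would be lost. That requires assuming that 10–20% of about 39 intervention starters (438 × 9%, before attrition) leave or fall silent before the next quarterly survey. No document gives such a rate, and it includes silent losses that an exit survey never reaches.
- A reader might note that one control start is about a quarter of that arm's expected events (1 of 3.9). The arithmetic is right, but the expected control loss in the table is only 0.04 to 0.22 starts.
- A reader might infer that leavers are counted as non-starters. Section 12.3 censors them.
- The sentence in Section 5.4, "Participant will then be withdrawn from study activities", might look like a general rule. It concerns only men who seroconvert, who are first invited to an interview that covers PrEP (Section 7.6).

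**Conclusion.** The gap is real but small, and of low severity. As written, a start between a man's last answered survey and his formal withdrawal is not captured. The expected loss is about 0.4 to 1.1 starts, or 2.3 with a full quarter's gap, out of about 39. This rests on the plan's own uptake and attrition figures, on leaving being unrelated to PrEP, and on the upper-end assumption that all attrition is formal withdrawal.

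The case for change is therefore not about power. It is that a contact already being made passes without reading the endpoint, and that the assumption behind the censoring cannot be examined among the men who leave.

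**What to change.** In Section 7.4, add the quarterly PrEP-use item, with month of start, to the withdrawal survey, worded identically in both arms. Section 4 already makes the quarterly surveys identical across arms (apart from final acceptability questions), so the item exists and avoids the differently worded monthly questions. After a positive answer, offer the existing DBS and photograph confirmation, on a voluntary basis.

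In Sections 3.2.1 and 12.3, state that the exit answer counts in the primary endpoint, with follow-up ending on that date, and that men who do not answer it are censored at their last completed assessment. Report completion of the exit item by arm.

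The cost is a slightly longer exit survey. No sample size or clinical procedure changes.

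Letting retention staff record the same item for non-responders who decline the full survey is optional. It adds a second mode of collection in an unblinded trial, at times driven by non-response that may differ by arm. If it is used, flag these answers by collection mode and examine them in a sensitivity analysis.

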#### 7.5 Unscheduled Visit

Any interaction with participants between scheduled visits will be considered unscheduled visits and will be tracked in SMART.

#### 7.6 In-depth Interviews

In-depth interviews: Up to 30 IDIs (approximately 10 per site) will be conducted within one month of PrEP initiation with men in the intervention arm who start PrEP. Up to 20 additional IDIs will be conducted within one month of study completion among men who fit the following criteria (N = maximum of 5 each): PrEP starters, PrEP non-starters, PrEP stoppers, and men that cycled on and off PrEP. IDI participants will be purposively sampled to ensure

representation of men who accessed the app at least one time during follow-up and received a PrEP recommendation. PrEP starters interviewed after one month of follow-up will not be reinterviewed at the end of study. The IDIs will be conducted by trained qualitative interviewers. We will develop semi-structured interview guides. Interviewers will receive training on the interview guides to ensure standardization across study sites. IDIs will assess the extent to which app components facilitated or inhibited PrEP uptake. Central to the IDI will be understanding the participants' use of the app. The IDI will begin by asking the participant to walk the interviewer through a "typical use session" of the app, during which the interviewer will probe around key decisions (e.g. why one function was used over other functions). The interview will examine the participant's views on the positive and negative elements of the app. The interview will focus on the use of PrEP components: participants will be asked to walk through the PrEP knowledge, screening and locating functions with the interviewer and describe why they did or did not use them. Participants who started PrEP will be asked to describe the role that the app played in their decision and which app components were most integral to their decision. They will be asked to demonstrate which components of the app were useful in adopting PrEP, and areas of the app where further support might be useful. Participants who did not start PrEP will be asked if there are additional components (e.g., better linkage to providers, other information) that could be added to the app that might lead them to change their mind about starting PrÉP. Participants who did not adopt PrEP will be asked to demonstrate how they used the app and which components of the app were not used. These data will provide insight into how the app is used in PrEP decision making, and identify areas of opportunity to promote PrEP adoption for future app versions.

Additional IDIs will be conducted with any participant who seroconverts during follow-up. These IDIs will follow a structure similar to those described above. Additional questions will be added to explore factors related to PrEP and seroconversion. Participants who were not on PrEP at the time of seroconversion will be asked why they did not initiate PrEP or why they discontinued PrEP if they had previously taken it. Patients who report being on PrEP at the time of seroconversion will be asked about adherence to the dosing regimen.

#### 8 STUDY PROCEDURES/EVALUATIONS

### 8.1 Study Procedures/Evaluations

Per-Protocol and Dose-Response Analyses: The primary efficacy analysis will be an intent-to-treat analysis. Because randomization to the intervention arm will not guarantee engagement with the HealthMindr app, we will use two types of secondary analysis to estimate the potential effects of the app under conditions of optimal adherence. First, a per-protocol analysis will estimate the effect of the app on rates of PrEP initiation under assumptions of substantial adherence using principal stratification methods to estimate the causal effects given associations between measured confounders and adherence profiles. Study subjects who participate in the baseline assessment and at least 3 subsequent monthly PrEP screeners during the year will be categorized as substantially adherent for this purpose. Second, level of engagement with the app, including number of times the app is opened per month or number of app features accessed per use, may vary strongly across participants. Under the hypothesis that greater engagement with the app will lead to faster initiation into PrEP, we will model the dose-response relationship between a continuous gradient of app engagement and rate of PrEP initiation among app users in the study.

# 8.2 Laboratory Procedures/Evaluations

**HIV Testing:** Participants in the intervention arm will be offered at-home HIV test kits up to 2 times during their 12 months of participation through the Emory CFAR. HIV is tested using FDA-approved OraQuick test using a mouth swab. Results can be verified through self-report.

**STI Testing:** Participants in the intervention arm will be offered at-home STI test kits up to two times during their 12 months of participation; through the Emory CFAR. Diagnosis of an STI is an indication for PrEP. The presence of C. trachomatis (CT) and N. gonorrhea (NG) in self-collected urethral, throat, and rectal specimens will be determined by using the Aptima Combo 2 CT/NG assay or Abbott Real Time CT/NG assay, an FDA-cleared real-time polymerase chain reaction (PCR) assay for direct, qualitative detection of a region of the cryptic plasmid DNA of CT and the Opa gene of NG. Syphilis screening will be conducted using the TREP-SURE EIA assay with reflexive rapid plasma reagin (RPR) test for reactive results; participants with a reactive result will be referred to a local provider for treatment and follow-up. Positive STI test results will be provided to participants over the phone by a study staff member who can refer participants to treatment. Upon request, copies of results may also be sent to the study participant.

**Alcohol and Substance Use Screening:** Residual urine from STI testing will be screened for alcohol and substance use. This will be done as a confirmation of self-report for substance use for research purposes only and results will not be reported back to participants. Participants who wish to receive referrals for assistance with substance use will be assisted with navigation services by study staff.

**Tenofovir detection**: Dried blood spot specimens from men who report initiating PrEP will be analyzed for intracellular concentrations of tenofovir diphosphate (TFV-DP) in the laboratory of [name], who directs the University of North Carolina CFAR Clinical Pharmacology Core. DBS cards are used to obtain a 3 mm "punch" which is eluted in a micro-centrifuge tube. The eluate is analyzed by liquid chromatography/tandem mass spectrometry. Tenofovir concentration is reported as fmol/10^6 RBCs; the lower limit of quantification is 2.5 ng/mL. Intracellular TFV-DP is commonly used as method of assessing adherence to PrEP; we will consider a positive result solely to corroborate self-report of PrEP initiation and photographic evidence of prescription. This will not be used to monitor adherence and results will not be returned to participants, as disclosed in the informed consent process.

#### 8.2.1 Specimen Shipment

#### Shipping CareKits to Participants

- 1. After the order is placed through the app, staff will place the kit order with the lab.
- 2. Kits will be mailed directly to the participant with instructions on how to register their kit online. This will allow staff to link the kit with the participant.

# Shipping Specimen

After collecting specimen(s) for testing, participants will indicate the date of collection and place specimens collected in the provided packaging, which meets all federal regulations for shipment of Biological Substances. Participants will ship their collected specimen(s) via USPS

to the designated laboratory via the provided pre-labeled mailer. Instructions on how to mail kits are included on an instructional sheet provided within the kit.

